3 STUDY OBJECTIVE(S) AND DESIGN

3.1 Study Objective(s)

3.1.1 Primary Objective

The primary objective of this study is to evaluate the effect of different doses and dosing regimens of ESN364 on frequency and severity of vasomotor symptoms (hot flashes).

3.1.2 Secondary Objectives

The secondary objectives of this study are the following:

- To evaluate the effect of different doses and dosing regimens of ESN364 on the frequency, severity, and hot flash score of mild, moderate, and severe vasomotor symptoms;
- To evaluate the effect of different doses and dosing regimens of ESN364 on responder rates using a variety of responder definitions;
- To evaluate the effect of different doses and dosing regimens of ESN364 on patient-reported outcomes;
- To evaluate the effect of different doses and dosing regimens of ESN364 on PD markers (hormone and bone markers); and
- To evaluate the effect of different doses and dosing regimens of ESN364 on safety and tolerability.

3.1.3 Exploratory Objectives

The exploratory objectives of this study are the following:

- CCI [REDACTED]
- To evaluate the PK plasma concentrations of ESN364 and metabolite CCI [REDACTED]

3.2 Study Design

This is a 12-week, randomized, double-blind, placebo-controlled, dose-ranging, parallel-group, multicenter study to assess the efficacy of ESN364 in postmenopausal women suffering from vasomotor symptoms (hot flashes).

This study will consist of a screening period (Days -35 to -1, including the screening visit [Visit 1] and a minimum 7-day collection of baseline vasomotor symptom frequency and severity assessments), a 12-week treatment period (Day 1 [Visit 2] to Week 12 [Visit 5], including safety visits at Week 2 [Visit 2A], Week 6 [Visit 3A], and Week 10 [Visit 4A]), and a follow-up visit (Week 15 [Visit 6]) approximately 3 weeks after the last dose of study drug, for a total of 9 visits.

The study will be performed on an ambulatory basis.

The screening visit (Visit 1) will occur up to 35 days prior to randomization. Eligibility will be assessed via a physical examination, clinical laboratory testing, vital signs, ECG, Pap

smear, mammography, and endometrial biopsy. Subjects will receive an electronic diary in which to record daily vasomotor symptoms during the duration of the screening period. Subjects must have ≥ 7 consecutive days of vasomotor symptom recordings to participate in the study. Subjects are encouraged to continue recording for the duration of the whole screening period. The electronic diary will be reviewed by study site staff on Day 1 (Visit 2) to confirm study eligibility. Subjects may be rescreened 1 time upon approval of the medical monitor. During the treatment period, subjects will return to the study site every 2 weeks for assessments. The follow-up visit will occur approximately 3 weeks following the last dose of study drug.

Approximately 352 subjects will be enrolled in the study. Subjects will be randomized to 1 of 8 treatment groups (i.e., 44 subjects in each arm).

Subjects and study personnel will be blinded to the treatment (placebo or ESN364), dosage (30 mg, 60 mg, etc.), and dosing regimen (QD or twice daily [BID]).

3.3 Randomization

In total, approximately 352 subjects will be randomized to 1 of 8 treatment groups in an equal ratio.

Randomization will be based on a computer-generated randomization schedule prepared by an unblinded biostatistician from Medpace Biostatistics using SAS[®] software (SAS Institute Inc., Cary, North Carolina, USA) prior to the start of the study. The randomization will be balanced using randomly permuted blocks across the treatment arms. The randomization list will be retained by Medpace Randomization and Study Product Management until the end of the study (database lock). A copy will be sent in a sealed envelope to the bioanalytical laboratory responsible for plasma drug and serum hormone determination before the start of the study as applicable. Because of a planned early timepoint analysis (see Section [7.9](#)) and because PK/PD modeling will start prior to database hard-lock, specific assigned Sponsor staff involved in these activities (or delegates, if outsourced to an external vendor) will be unblinded after recruitment has been completed. Details of the unblinding will be documented in a separate charter to ensure the direct study team remains blinded and that unblinded results are restricted to a very small group independent of the study team.

Subjects will be assigned a randomization number from the Interactive Response Technology (IRT) system upon enrollment. The randomization list will be uploaded into the IRT system. Based on this randomization list, the study drug will be packaged and labeled. Medication numbers will be preprinted on the study drug labels. The study team, including those involved in data management, clinical, medical, or statistical review of the study data, will also be blinded during the study as they will not have access to the randomization list. Medpace, the Contract Research Organization (CRO) performing data management and statistical activities, will receive a copy of the randomization list after database lock. The study drug administered to a subject can be identified by the IRT system. The IRT system will allow rapid access to the treatment allocation codes when relevant for site or CRO personnel.

4 SAMPLE SIZE

A total of 352 subjects are planned to be randomized, 44 subjects in each treatment arm.

In the Phase 2a study, the observed least-squares mean difference between ESN364 90 mg BID (highest dose of this Phase 2b study) and placebo in change from baseline to Week 12 in mean daily frequency of moderate to severe vasomotor symptoms was -5.0 (95% CI: - 6.8, -3.3) with similar results at Week 4. For any given pairwise comparison for a 2-sample t-test at a 2-sided 5% alpha, 40 subjects provides the following power to detect the following effect sizes assuming an SD of 5:

Assumed treatment difference in mean daily frequency	Power for pairwise test
3.3	83%
3.5	87%
4	94%
4.5	97%
5	>99%

For change from baseline to Week 12 in mean severity of moderate to severe vasomotor symptoms, the observed mean treatment difference in the Phase 2a study was -1.12 (95% CI: -1.5, -0.74) with similar results at Week 4. For any given pairwise comparison for a 2-sample t-test at a 2-sided 5% alpha, 40 subjects provides the following power to detect the following effect sizes assuming an SD of 1:

Assumed treatment difference in mean severity	Power for pairwise test
0.64	80%
0.75	91%
1	>99%

Note that the combined power for testing all 4 co-primary endpoints will be lower than the power for each considered individually. Assuming approximately 10% of subjects discontinue prematurely, the number of 40 subjects is increased to 44 subjects per arm.

5 ANALYSIS SETS

In accordance with International Conference on Harmonization (ICH) recommendations in guidelines E3 and E9, the following analysis sets will be used for the analyses.

Detailed criteria for analysis sets will be laid out in Classification Specifications (CS) and the allocation of subjects to analysis sets will be determined prior to database hard lock.

All primary and secondary efficacy endpoints will be analyzed using the Full Analysis Set (FAS). The Per Protocol Analysis Set (PPS) will be used only for the analysis of selected endpoints to examine the robustness of the primary analysis. Safety and tolerability will be analyzed using the Safety Analysis Set (SAF).

5.1 Safety Analysis Set (SAF)

The SAF comprises all randomized subjects who received at least one dose of study drug. The SAF will analyze patients as treated. In case a subject erroneously received a treatment different from her randomized treatment, the subject will be assigned to the treatment group

that the subject received as first dose. The SAF will be used for summaries of demographic and baseline characteristics and all safety and tolerability related variables.

5.2 Full Analysis Set (FAS)

The FAS comprises the subset of subjects from the SAF who received at least one dose of study drug, had a baseline and at least one post-baseline efficacy evaluation. The FAS will analyze patients as randomized, irrespective of the actual treatment received. The FAS will be used for summaries and primary analyses of efficacy data, as well as selected demographic and baseline characteristics.

5.3 Per Protocol Analysis Sets (PPS)

The PPS comprises the subset of subjects from the FAS who are treated according to the protocol without any major deviations. A full detail of inclusions and exclusions from Per Protocol Analysis Set - Week 4 (PPS4) and Per Protocol Analysis Set - Week 12 (PPS12) will be in the classifications specifications and finalized before unblinding.

5.3.1 Reasons for Exclusion From PPS4

The following reasons may lead to subject's exclusion from PPS4:

- No measurement of the primary efficacy endpoint available at Week 4.
- <85% interactive diary compliance during the 4 week treatment period.
- Treatment compliance less than or equal to 85% between randomization and Week 4.

5.3.2 Reasons for Exclusion From PPS12

The following reasons may lead to subject's exclusion from PPS12:

- No measurement of the primary efficacy endpoint available at Week 12.
- <85% interactive diary compliance during the 12 week treatment period.
- Treatment compliance less than or equal to 85% between randomization and Week 12.

5.4 Pharmacokinetics Analysis Set (PKAS)

The PKAS comprises the subset of subjects who receive study drug and provide at least one sample for the measurement of drug concentrations. Exclusion of subjects from the PKAS will be considered by the pharmacokineticist on a case-by-case basis.

6 ANALYSIS VARIABLES

6.1 Efficacy Endpoints

6.1.1 Co-Primary Efficacy Endpoints

The primary efficacy objectives will require the evaluation of the effect of ESN364 on the following 4 co-primary endpoints:

- Mean change in the frequency of moderate to severe vasomotor symptoms from baseline to Week 4;

- Mean change in the frequency of moderate to severe vasomotor symptoms from baseline to Week 12;
- Mean change in the severity of moderate to severe vasomotor symptoms from baseline to Week 4; and
- Mean change in the severity of moderate to severe vasomotor symptoms from baseline to Week 12.

Subjects will record the number of vasomotor symptoms and severity of each vasomotor symptom via the ePRO diary from the screening visit (Days -35 to -1 [Visit 1]) through the follow-up visit (Week 15 [Visit 6]).

Night sweats (vasomotor symptoms that disrupt the subject's night sleep) should be recorded no later than in the morning upon awakening to start a new day. Subjects should take note of the time of the night sweat and record it on the appropriate calendar day (i.e., before or after midnight).

The 24 hour vasomotor symptoms runs from 08:00 AM to 07:59 AM (next day); the 12 hour day time vasomotor symptoms is between 08:00 AM and 07:59 PM; the 12 hour night time vasomotor symptoms is between 08:00 PM and 07:59 AM (next day) regardless of whether the patient was awake or woke up because of the event.

Frequency of moderate to severe vasomotor symptoms is the number of moderate to severe vasomotor symptoms per 24h (or 12h day time or 12h night time).

The severity of vasomotor symptoms is defined clinically as follows (according to the FDA and European Medicines Agency Guidances for Industry^{1,2} and the National Institutes of Health [NIH] Hot Flash Workshop³):

- Mild: Sensation of heat without sweating/dampness. If at night, subject does not wake up but later notices damp sheets or clothing.
- Moderate: Sensation of heat with sweating/dampness, but able to continue activity. If at night, subject wakes up because she is feeling hot and/or is sweating, but no action is necessary other than rearranging the bed sheets.
- Severe: Sensation of intense heat with sweating, causing disruption of activity. If at night, subject wakes up hot and is sweating and needs to take action (e.g., remove layers of clothes, open the window, or get out of bed).

The severity of moderate and severe vasomotor symptoms per 24h (or 12h day time or 12h night time):

$$\frac{[(\text{number of moderate vasomotor symptoms} \times 2) + (\text{number of severe vasomotor symptoms} \times 3)]}{\text{number of moderate/severe vasomotor symptoms}}$$

Severity is zero for subjects who have no moderate or severe vasomotor symptoms.

A daily frequency and severity per week will be derived by taking the mean of the data over 7 days. A daily average per week will be derived if any information for 3 or more days was reported (morning dose, evening dose, or vasomotor symptom).

Because baseline data is preferably the most recent data prior to randomization and dosing, baseline for this study is the mean value of vasomotor symptoms calculated over the last 7 calendar days with non-missing data prior to Day 1 (Visit 2). As a consequence, the baseline might be less than the required 50 moderate/severe hot flashes per week required for study entry, as these can occur anywhere during the 35 day screening period provided that they are the last 7 days with non-missing data prior to Day 1 (Visit 2).

See Section [7.10.6](#) for study week and endpoint derivations.

6.1.2 Secondary Efficacy Endpoints

The secondary efficacy endpoints include the effect of ESN364 on the following:

6.1.2.1 Vasomotor Symptom Endpoints:

- Mean change in the frequency of mild, moderate, and severe vasomotor symptoms from baseline to each study week;
- Mean change in the frequency of moderate and severe vasomotor symptoms per 24h from baseline to each study week;
- Mean change in the severity of mild, moderate, and severe vasomotor symptoms from baseline to each study week;
- Mean change in the severity of moderate and severe vasomotor symptoms from baseline to each study week;
- Mean change in the hot flash score of mild, moderate, and severe vasomotor symptoms from baseline to each study week;
- Mean change in the hot flash score of moderate and severe vasomotor symptoms from baseline to each study week;
- Mean percent reduction of mild, moderate, and severe vasomotor symptoms from baseline to each study week; and
- Mean percent reduction of moderate and severe vasomotor symptoms from baseline to each study week.

Frequency of mild, moderate and severe vasomotor symptoms is the number of mild, moderate and severe vasomotor symptoms per 24h (or 12h day time or 12h night time).

Severity of mild, moderate and severe vasomotor symptoms per 24h (or 12h day time or 12h night time):

$$\frac{[(\text{number of mild vasomotor symptoms} \times 1) + (\text{number of moderate vasomotor symptoms} \times 2) + (\text{number of severe vasomotor symptoms} \times 3)]}{\text{number of mild/moderate/severe vasomotor symptoms}}$$

Severity is zero for subjects who have no hot flashes.

Hot flash score per 24h (or 12 h day time or 12 h night time): The hot flash score per 24h (or 12 h day time or 12 h night time) of vasomotor symptoms (mild, moderate, and severe) is calculated as follows:

(number of mild vasomotor symptoms x 1) +
(number of moderate vasomotor symptoms x 2) +
(number of severe vasomotor symptoms x 3).

The hot flash score per 24h (or 12 h day time or 12 h night time) of moderate and severe vasomotor symptoms is calculated as follows:

(number of moderate vasomotor symptoms x 2) +
(number of severe vasomotor symptoms x 3).

A weekly frequency, severity, or hot flash score will be derived similar to the co-primary efficacy endpoints. See Section 7.10.6 for study week and endpoint derivations.

6.1.2.2 Responder Endpoints:

- Mean percent reduction of 50%, 70%, 90%, and 100% of mild, moderate, and severe vasomotor symptoms from baseline to each study week;
- Mean percent reduction of 50%, 70%, 90%, and 100% of moderate and severe vasomotor symptoms from baseline to each study week;
- Absolute reduction of 2, 3, 4, and 5 in mean number of mild, moderate, and severe vasomotor symptoms per 24h from baseline to each study week; and
- Absolute reduction of 2, 3, 4, and 5 in mean number of moderate and severe vasomotor symptoms per 24h from baseline to each study week.

6.1.2.3 Patient-Reported Outcome Endpoints:

- Change in Hot Flash Related Daily Interference Scale (HFRDIS) from baseline to Weeks 4, 8, 12, and 15;
- Change in Leeds Sleep Evaluation Questionnaire (LSEQ) from baseline to Weeks 4, 8, 12, and 15;
- Change in Greene Climacteric Scale (GCS) from baseline to Weeks 4, 8, 12, and 15; and
- Change in Menopause-Specific Quality of Life (MENQoL) from baseline to Weeks 4, 8, 12, and 15.

HFRDIS: The HFRDIS is a 10-item scale that measures a woman's perceptions of the degree to which vasomotor symptoms interfere with 9 daily life activities (work, social activities, leisure, sleep, mood, concentration, relations with others, sexuality, and enjoying life); the 10th item measures interference with overall quality of life.⁵ This scale was modeled after items on the Brief Pain Inventory⁶ and Brief Fatigue Inventory,⁷ which assess the extent to which pain or fatigue interfere with daily life. Subjects will be asked to rate the extent to which vasomotor symptoms have interfered with each item during the previous 2-week time interval using a 0 (do not interfere) to 10 (completely interfere) scale. Recent structural equation modeling suggests the HFRDIS is a unidimensional scale best represented by an overall mean score calculated as the sum of items/10.⁸ If any of the 10 items have missing values, the overall mean score will not be calculated.

LSEQ: The LSEQ is a 10-item self-rated questionnaire that assesses a subject's aspects of sleep and early morning behavior. The questions are grouped into 4 chronological domains: ease of getting to sleep (items 1 to 3), perceived quality of sleep (items 4 to 5), ease of

awaking from sleep (items 6 to 7) and integrity of early morning behavior following wakefulness (items 8 to 10).⁹ The LSEQ is a visual analogue scale that requires respondents to place marks on a group of 10 cm lines representing the changes they have experienced in a variety of symptoms compared to usual (baseline version) versus since the beginning of treatment (post-baseline version). Lines extend between extremes like “more difficult than usual” and “easier than usual.” Responses are measured using a 100 mm scale and are averaged to provide a score for each domain. Note the questionnaire was reformatted for data collection to ensure precise measurements. Visit 2 data not collected on the baseline version of the LSEQ will be excluded from the analysis and listings. If any of the responses in a domain have missing values, the score for the domain will not be calculated.

GCS: The GCS is a 21-item scale that provides a brief but comprehensive and valid measure of climacteric symptomatology.¹⁰ Each item is rated by the subject according to its severity using a 4-point rating scale from 0 (none) to 3 (severe). The first 20 items of the scale combine into 3 main independent symptom measures by summing up the individual item scores:

- Psychological symptoms (items 1 to 11; score 0 to 33),
- Physical symptoms (items 12 to 18; score 0 to 21), and
- Vasomotor symptoms (items 19 to 20; score 0 to 6).

Item 21 is a probe for sexual dysfunction. The total score can range from 0 to 63. Higher scores indicate worse symptoms. If any of the contributing items have missing values, scores for psychological symptoms, physical symptoms, or vasomotor symptoms will not be calculated. If any of the scores for psychological symptoms, physical symptoms, or vasomotor symptoms are missing, the total score will not be calculated.

MENQoL: The MENQoL is a self-administered questionnaire and consists of a total of 29 items in a Likert-scale format. Each item assesses the impact of 1 of 4 domains of menopausal symptoms, as experienced over the last month:

- Vasomotor (items 1 to 3),
- Psychosocial (items 4 to 10),
- Physical (items 11 to 26), and
- Sexual (items 27 to 29).

Items pertaining to a specific symptom are rated as present or not present, and if present, how bothersome on a 0 (not bothersome) to 6 (extremely bothersome) scale.^{11,12} Non-endorsement of an item is scored a “1” and endorsement a “2” plus the number of the particular rating, so that the possible score of any item ranges from 1 to 8.¹² Mean scores are computed for each domain by dividing the sum of the domain’s items by the number of items within that domain.¹³ The overall mean score is the mean of the domain mean scores. If any of the contributing items have missing values, the mean score for the domain will not be calculated. If any of the domain mean scores are missing, the overall mean score will not be calculated.

For all patient reported outcome endpoints, baseline is the value at Day 1 (Visit 2).
Questionnaires are completed at site prior to any invasive procedures are completed.

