8.1.2 Hot Flash Related Daily Interference Scale

Perceived vasomotor symptom interference on daily activities will be evaluated at Day 1 (Visit 2), Week 4 (Visit 3), Week 8 (Visit 4), Week 12 (Visit 5)/ET, and the follow-up visit (Week 15 [Visit 6]) using the HFRDIS. The HFRDIS will be paper-based and administered at the study site prior to any invasive procedures.

The HFRDIS is a 10-item scale that measures a woman's perceptions of the degree to which vasomotor symptoms interfere with 9 daily life activities (work, social activities, leisure, sleep, mood, concentration, relations with others, sexuality, and enjoying life); the 10th item measures interference with overall quality of life.²⁶ This scale was modeled after items on the Brief Pain Inventory²⁷ and Brief Fatigue Inventory,²⁸ which assess the extent to which pain or fatigue interfere with daily life. Subjects will be asked to rate the extent to which vasomotor symptoms have interfered with each item during the previous 2-week time interval using a 0 (do not interfere) to 10 (completely interfere) scale. Recent structural equation modeling suggests this is a unidimensional scale best represented by an overall mean score (sum of items/10).²⁹

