- r. Samples to be taken Week 4 (Visit 3) predose and 1 h (± 30 min), 3 h (± 30 min), 5 h (-1 h/+30 min), and 7 h (-1 h/+2 h) postdose as well as predose Week 12 (Visit 5). The indicated time windows for Week 4 (Visit 3) PK sampling will allow for flexibility.
- s. While scheduled for Week 12 (Visit 5), the PGX sample can be taken at any time during the study following signed informed consent and enrollment into the study.
- t. The vasomotor symptom diary will be kept by subjects. Subjects will record the vasomotor symptom frequency and severity of each vasomotor symptom in the ePRO diary on an ad hoc basis, but at a minimum twice daily (morning and evening), from the screening visit (Days -35 to -1 [Visit 1]) through the follow-up visit (Week 15 [Visit 6]). Night sweats should be recorded no later than in the morning upon awakening to start a new day.
- u. Paper-based, administered at the study site prior to any invasive procedures.
- v. A baseline LSEQ assessment will be collected at Day 1 (Visit 2). A post-baseline LSEQ assessment will be collected for all other indicated visits.
- w. CC/ 
- x. Includes BALP, P1NP, and CTX.

Footnotes continued on next page

- y. Subjects will be assigned 2 bottles of study drug as a kit (1 bottle labeled “morning” and 1 bottle labeled “evening”) at Day 1 (Visit 2), Week 4 (Visit 3), and Week 8 (Visit 4). Each bottle will contain 34 capsules of ESN364 or placebo. Study drug intake will be done with a glass of room temperature tap water. The first intake of study drug will take place at the study site on Day 1 (Visit 2) between 7:00 AM and 10:00 AM, under the supervision of the study staff. On study visit days (Day 1 [Visit 2], Week 4 [Visit 3], and Week 8 [Visit 4], only), the morning dose of study drug will be taken at the study site, under the supervision of the study staff, after collection of predose blood samples. Subjects will be instructed to arrive at the study site fasted (nothing by mouth except water [up to 1 hour prior to study drug intake] for at least 10 hours). On all other days throughout the treatment period, subjects will be instructed to take their morning dose of study drug at home, around the same time of the day spaced as near to 12 hours apart as possible (preferably between 7:00 AM and 10:00 AM and 7:00 PM and 10:00 PM). Intake of study drug should be preferably 1 hour before or 2 hours after meals. Subjects need to record all home study drug intake in the ePRO diary.

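### One blank item voids a patient-reported score, so nearly complete paper forms are discarded; score the longer scales from answered items and keep the complete-item score as sensitivity

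*SAP*

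**What the plan says.** SAP 6.1.2.3 (Patient-Reported Outcome Endpoints) sets these rules:

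- **HFRDIS**, 10 items: "If any of the 10 items have missing values, the overall mean score will not be calculated".
- **LSEQ**, domains of 3, 2, 2 and 3 items: "If any of the responses in a domain have missing values, the score for the domain will not be calculated". No LSEQ total is defined.
- **GCS**, subscales of 11, 7 and 2 items plus item 21: "If any of the contributing items have missing values, scores for psychological symptoms, physical symptoms, or vasomotor symptoms will not be calculated". The total follows, since it is also lost if any of the scores for psychological "symptoms, physical symptoms, or vasomotor symptoms are missing, the total score will not be calculated".
- **MENQoL**, domains of 3, 7, 16 and 3 items: "If any of the contributing items have missing values, the mean score for the domain will not be calculated". One level up, "If any of the domain mean scores are missing, the overall mean score will not be calculated".

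The schedule in SAP 2.2 describes the forms as "Paper-based, administered at the study site prior to any invasive procedures". Baseline for all four is the Day 1 form. SAP 7.4.2 analyses the scores on the FAS with the MMRM of SAP 7.4.1.2, which has the baseline value as a covariate. SAP 7.10.1 plans multiple imputation for missing primary endpoints and non-responder imputation for binary variables, but nothing for questionnaire items.

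**The concern.** A woman who answers 9 of 10 HFRDIS items or 28 of 29 MENQoL items is treated, for the full score, like one who returned no form. The answers she gave are dropped, and precision is lost on endpoints that serve a stated secondary objective in arms of only 44.

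The rule is also much stricter than the one for the diary. SAP 6.1.1 derives a weekly mean when there is information for 3 or more of 7 days, so 4 days may be missing, whereas a questionnaire score may miss nothing.

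The Day 1 form matters most. A void there leaves no baseline, so no change score exists at any visit for that scale. SAP 7.10.6 lets a screening value stand in for a missing baseline, but the schedule has no questionnaire at screening, so that fallback is empty.

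**Working it through.** **Figure in the plan.** There is none on this point. Neither document states an item-blank rate, an expected questionnaire completeness or a power for these endpoints. SAP section 4 covers the co-primary endpoints only. Its table reproduces: for 40 per arm and SD 5, a two-sample t-test gives 83.0% power for a difference of 3.3 (stated 83%) and 94.2% for 4 (stated 94%). Nothing below changes those figures.

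**Inputs.** The item counts k come from SAP 6.1.2.3. The chance p that an item is blank is assumed at 0.5%, 1% and 2%.

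**Loss per form, independent blanks.** P(score void) = 1 − (1 − p)^k. For HFRDIS at 1%: 1 − 0.99^10 = 9.6%.

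| Score | k | 0.5% | 1% | 2% |
|---|---|---|---|---|
| HFRDIS mean | 10 | 4.9% | 9.6% | 18.3% |
| GCS total | 20 | 9.5% | 18.2% | 33.2% |
| MENQoL overall | 29 | 13.5% | 25.3% | 44.3% |
| MENQoL physical | 16 | 7.7% | 14.9% | 27.6% |
| GCS psychological | 11 | 5.4% | 10.5% | 19.9% |
| 7-item domain (GCS physical, MENQoL psychosocial) | 7 | 3.4% | 6.8% | 13.2% |
| 3-item domain | 3 | 1.5% | 3.0% | 5.9% |
| 2-item domain | 2 | 1.0% | 2.0% | 4.0% |

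On 44 forms at p = 1%, about 4 HFRDIS means (44 × 0.096), 8 GCS totals (44 × 0.182) and 11 MENQoL overall means (44 × 0.253) would be void.

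**How complete the voided forms are.** The share of voided forms with exactly one blank is k·p·(1 − p)^(k−1) divided by the loss. For the three full scores it runs from 95.5% (HFRDIS at 1%) down to 74.3% (MENQoL at 2%).

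**Clustered blanks.** If blanks concentrate in a few forms, fewer forms are hit. With a beta-binomial model, a = p(1 − ρ)/ρ and b = (1 − p)(1 − ρ)/ρ, the loss is 1 − B(a, b + k)/B(a, b), where B is the beta function:

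| ρ (assumed) | p | HFRDIS | GCS total | MENQoL overall |
|---|---|---|---|---|
| 0.1 | 1% | 6.8% | 10.3% | 12.5% |
| 0.1 | 2% | 13.1% | 19.7% | 23.6% |
| 0.3 | 1% | 4.2% | 5.6% | 6.4% |
| 0.3 | 2% | 8.3% | 10.9% | 12.3% |

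**Loss if domains of three or more items are scored when at least half are answered** (independent blanks, 1% / 2%). HFRDIS falls to effectively zero. MENQoL overall falls to 0.06% / 0.24%, nearly all of it from the two 3-item domains: 2 × [3p²(1 − p) + p³]. If the two-item GCS vasomotor subscale still needs both items, the GCS total loses about 1 − (1 − p)² = 2.0% / 4.0%.

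**GCS item 21.** The subscale maxima add to 33 + 21 + 6 = 60. The stated total range of 0 to 63 therefore needs item 21, worth 3 points. The missing-item rule names only the three subscales, so the plan does not say what happens to the total when item 21 is blank.

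**The case against.** The rule is prespecified, clear and the same in every arm. It follows the protocol's own formulas, which divide by the full number of items (Protocol 8.1.2 and 8.1.5). The forms are completed at the site, and Protocol 11.1.5 refers missing data back for query. All of that stands. However, no completeness check before the subject leaves is described, and a later query recovers a 2-week or one-month self-rating poorly.

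A reader might go further than the documents allow in four ways:

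- **That 10% to 40% of forms will be lost.** No document gives a blank rate. Losses of that size need 1% to 2% blanks that are nearly independent, and they apply only to the full scores and the longer domains.
- **That one blank always voids a whole questionnaire.** For LSEQ it costs one domain of four. GCS and MENQoL keep their unaffected subscales and domains.
- **That the loss is selective, removing women for whom an item does not apply.** All three scales offer a valid null answer: not present on MENQoL, none on GCS, and no interference on HFRDIS. Selection remains possible, for example on the HFRDIS work or sexuality items, but it is not shown.
- **That change scores lose twice as much.** Squaring the completion probability assumes independence between visits. Women who skip the same item each time would break that assumption. In the MMRM a void post-baseline score costs one visit, not the subject.

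The half rule is also not free of objection. On a two-item domain it would rest the score on one answer.

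**Conclusion.** The point holds as a cheap improvement to secondary endpoints. The all-or-nothing rule is certain from the text; the size of the loss is not, because it depends on an assumed blank rate and on how blanks cluster. Across the cases worked here with 1% to 2% of items blank, the three full scores lose between 4% and 44% of forms, and two- and three-item domains lose 2% to 6% under independence. Most of the full scores lost under independence come from forms with a single blank.

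In the MMRM a void Day 1 score is the costly case, since it removes the subject for that score. The step-down test, the co-primary power and the sample size are untouched. No bias in the treatment comparison has been demonstrated; what is at stake is avoidable loss of precision, and an undefined GCS total when item 21 is blank.

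**What to change.** Amend SAP 6.1.2.3 before unblinding:

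1. Score HFRDIS as the mean of the answered items when at least half are answered.
2. Apply the same rule to LSEQ and MENQoL domains and GCS subscales with three or more items. For GCS, prorate the sum: answered sum × items in subscale ÷ items answered.
3. Keep the complete-item rule for the two-item domains (LSEQ quality of sleep, LSEQ awakening, GCS vasomotor).
4. Compute the GCS total and the MENQoL overall mean when all component scores exist, and state what a blank GCS item 21 does to the total.
5. Report the complete-item version of every score as a sensitivity analysis, with the number of forms voided per arm and visit.

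The cost is SAP wording and a second set of score derivations, with no new data. The price is one assumption: unanswered items resemble the answered ones in the same domain. The documents support this directly only for HFRDIS, where Protocol 8.1.2 says "Recent structural equation modeling suggests this is a unidimensional scale best represented by an overall mean score". It is weaker for mixed domains such as MENQoL physical, which is why the complete-item analysis should stay.
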